Trial unblinding and transition from the randomized observer-blinded phase to the open-label phase will be conducted on a country/site level, depending on full competent authority and Ethics Committee approval of Protocol version 4.0 per country/site.
Trial Visits/For subjects participating in Phase 2b Immunogenicity Subset (see Table 1):
 o 7 protocol-scheduled site visits on Day 1, Day 29, Day 43, Day 57, Day 120, Day 211, and Day 393.
 3 protocol-scheduled phone contacts (safety calls) on Day 2, Day 30, and Day 302.
For subjects participating in Phase 2b non-immunogenicity (see Table 2):
 6 protocol-scheduled site visits on Day 1, Day 29, Day 43, Day 120, Day 211, and Day 393.
 4 protocol-scheduled phone contacts (safety calls) on Day 2, Day 30, Day 57, and Day 302.
For subjects participating in the randomized observer-blinded Phase 3 (see Table 3):
 5 protocol-scheduled site visits on Day 1, Day 29, Day 43, Day 211, and Day 393.
 3 protocol-scheduled phone contacts (safety calls) on Day 57, Day 120, and Day 302.

	After trial unblinding:	
	Subjects of the placebo treatment arm will be notified of the trial treatment they received by a Subject Information Letter and will be withdrawn after an EOT phone call. Subjects of the CVnCoV treatment arm will be notified of the trial treatment they received at the next planned trial visit/phone call.	
	For subjects participating in the Open-label Phase:	
	Cohort A: CVnCoV-AV (Table 4) and Cohort B: CVnCoV only (Table 5):	
	 Phone calls or clinic visits will be performed after trial unblinding on Day 302 and Day 393/EOT of the original Phase 2b/3 schedule. 	
Collection of Blood Samples:	The maximum total volume of blood taken over the trial period from any subject is 304 mL.	
Safety Assessments:	The safety and reactogenicity of a 2-dose schedule of CVnCoV will be assessed by measuring the frequency and severity of the following AEs as described below.	
	Safety assessments specific for subjects in Phase 2b:	
	 Reactogenicity will be assessed daily on each vaccination day and the following 7 days by collection of solicited local AEs (injection site pain, redness, swelling, and itching) and solicited systemic AEs (fever, headache, fatigue, chills, myalgia, arthralgia, nausea/vomiting, and diarrhea) using electronic diaries (eDiaries). In addition, other indicators of safety will be collected (e.g., body temperature). 	

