a. The open-label phase visits should be scheduled according to the originally scheduled visits/phone calls in the Phase 2b/3 schedule: Day 302 (-3/+21 days) and Day 393 (-0/+21 days). After trial unblinding, the Day 302 and Day 393 visits will be performed as phone calls, but a clinic visit may be performed if ICF signature cannot be done via e-mail, phone call, or mail.

If the Day 302 phone call was already performed as part of the randomized observer-blinded phase before approval of Protocol version 4.0, the ICF will be signed at the Day 393/EOT phone call/visit.

Subjects of the CVnCoV treatment arm who already received or plan to receive an AV are eligible for this cohort. The AV should be recorded in the eCRF.

Clinical Trial Protocol	CV-NCOV-004
CureVac AG	COVID-19 mRNA Vaccine

- b. Roll-over criteria for the open-label phase should be reviewed and confirmed on Clinic Visit OL-1.
- c. Vaccination history should be checked to establish eligibility. If the subject did not report any administration of a COVID-19 AV, he/she needs to be asked whether he/she received a COVID-19 AV already and, if confirmed, the AV needs to be documented in the eCRF.
- d. SAEs, AESIs, and AEs leading to trial discontinuation will be collected until the EOT.

During all site visits, trial staff will remind subjects to call the site immediately to report the following: if he/she experiences any concerning medical event; or experiences a serious medical event, has a change in overall health, or is diagnosed with a new medical condition by a doctor. These should be reported regardless of the perceived relationship between the event and the trial vaccine.

COVID-19 AV vaccination details (specific AV and vaccination dates) will be collected.

- e. Medications for AESIs, or SAEs, and any immune-suppressive/modulating medications will be documented in the eCRF for the time period specified Table 6. Any prohibited medication (as defined in Section 7.6.2) taken by the subject also needs to be documented in the eCRF.
- f. During all site visits/phone calls, trial staff will remind subjects to report any confirmed COVID-19 positive tests.

Clinical Trial Protocol	CV-NCOV-004
CureVac AG	COVID-19 mRNA Vaccine

Table 5 Schedule of Trial Assessments and Procedures for the Open-label Phase: Cohort B: CVnCoV only

	Follow-up Period	End of Trial
	Phone Call/Clinic Visit ^a	Phone Call/Clinic Visit
Clinic Visit Number	OL-1	OL-2
Visit Window (days)	-3/+21	-0/+21

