7.3.3.2 Trial Unblinding

Since the efficacy results from the HERALD trial are available and subjects in this trial are currently allowed to receive an AV, all subjects in this trial will be unblinded. Unblinding will be performed by country/site depending on full Competent Authority and Ethics Committee approval of Protocol version 4.0 per country/site.

The CRO will provide the sites with the subject numbers potentially eligible for each cohort. Each subject will be informed by the Investigator of the available results and whether he/she received CVnCoV or placebo in the trial (see Section 9.1.4).

Subjects who received at least 1 dose of CVnCoV will be asked to remain in the trial to allow safety follow-up. Subjects who received placebo will be withdrawn after trial unblinding.

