9.1.4 Open-label Phase

The open-label phase will start immediately after regulatory and ethical approval was obtained for Protocol version 4.0 on country/site level. Sites will be provided with a list of treatment assignments for subjects who are still blinded at the timepoint of trial unblinding.

The eDiary app will no longer be used during the open-label phase.

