9.1.4.1 Subjects who Received CVnCoV: Cohorts A and B

Subjects in the CVnCoV treatment arm who did not yet receive an AV will have to decide whether they will opt to receive an AV in addition to CVnCoV. Subjects of the CVnCoV treatment arm will be included in Cohort A if they received an AV after individual unblinding or will receive an AV after trial unblinding. Subjects will be included in Cohort B if they have not received and do not receive any AV until the EOT.

Subjects who initially intend to complete the trial without receiving an AV and later decide to receive an AV within the open-label phase will be switched to Cohort A.

All subjects who received CVnCoV and continue in the open-label phase will sign a new ICF after trial unblinding.

The open-label phase visits should be scheduled according to the originally scheduled visits/phone calls in the Phase 2b/3 schedule: Day 302 (-3/+21 days) and Day 393 (-0/+21 days). After trial unblinding, the Day 302 and Day 393 visits will be performed as phone calls, but a clinic visit may be performed if ICF signature cannot be done via e-mail, phone call, or mail.

9.1.4.1.1 Phone Call/Clinic Visit OL-1: Day 302 of the Original Phase 2b/3 Schedule (-3/+21 days)

During this visit, a new ICF will be obtained. If the Day 302 phone call was already performed as part of the randomized observer-blinded phase before approval of Protocol version 4.0, the ICF will be signed at the Day 393/EOT phone call/clinic visit.

Subjects in the CVnCoV treatment arm who already received or plan to receive an AV are eligible for Cohort A. The AV should be recorded in the eCRF.

The following assessments should be performed:

- Obtain the signed ICF: A new signed informed consent must be obtained after trial unblinding (see Section 12.4).
- For Cohort A: Confirm choice for AV.
- Review roll-over criteria for the open-label phase (see Section 6.3).
- Record concomitant medications and vaccinations (including COVID-19 AV vaccination) since last visit or phone call, according to instructions in Section 7.6.

Clinical Trial Protocol	CV-NCOV-004
CureVac AG	COVID-19 mRNA Vaccine

- Review and record any newly reported AEs since the last site visit or phone call (e.g., SAEs, AESIs, AEs leading to trial discontinuation).
- If the subject reports any concerning AEs, these should be followed-up either by a phone call(s) or by an unscheduled site visit based on the judgment of the Investigator.
- Instructions for the subjects:

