 - Remind the subject to call the site immediately to report the following:
 - If he/she experiences any concerning medical event.
 - Experience a serious medical event, have a change in overall health or be diagnosed with a new medical condition by a doctor. These should be reported regardless of the perceived relationship between the event and the trial vaccine.
 - Remind the subject to report any confirmed COVID-19 positive test, or in case sites continue to perform the test, remind the subject to call the Investigator in case of new symptoms according to the more restrictive definition used for the open-label phase (see Section 9.2.1.3.1).
- Complete the source documents and eCRF for this visit.

9.1.4.1.2 End of Trial Phone Call/Clinic Visit OL-2: Day 393 of the Original Phase 2b/3 Schedule (-0/+21 days)

The EOT phone call/clinic visit will be performed on Day 393, approximately 1 year after the last CVnCoV administration.

The following assessments should be performed:

- If the Day 302 phone call was already performed as part of the randomized observer-blinded phase before approval of Protocol version 4.0, the ICF will be signed at the Day 393/EOT phone call/clinic visit.
- Review and record any newly reported AEs since the last site visit or phone call (e.g., SAEs, AESIs).
- Record concomitant medications and vaccinations (including COVID-19 AV vaccination for Cohort A) according to instructions in Section 7.6.
- Complete the source documents and eCRF for this visit.

Inform the subjects that they have completed the trial.

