9.1.4.2 Placebo Subjects

Subjects of the placebo treatment arm will be notified of the trial treatment they received by a Subject Information Letter and they will be withdrawn after an EOT phone call. In case the subject needs to attend the site around the time of unblinding, a visit may be performed instead of the phone call.

Before the EOT phone call, the subject's medical records and eCRF need to be reviewed to identify any potential ongoing SAE or AESI.

Clinical Trial Protocol	CV-NCOV-004
CureVac AG	COVID-19 mRNA Vaccine

At the EOT phone call, any follow-up information on SAEs and AESIs needs to be documented. Subjects further need to be asked for any new SAE or AESI since the last trial contact and if any, those need to be documented.

The subject should be informed that the e-diary app can now be deleted and that no further tracking for COVID-19 is possible within the trial after the subject was withdrawn.

The EOT phone call will be documented in the subject's medical records, and the End-of-Trial form in the eCRF will be completed.

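### Still-blinded CVnCoV subjects whose Day 302 call preceded version 4.0 approval are, by the planned route, told their treatment only at trial exit, with no scheduled AV advice

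*Protocol*

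**What the plan says.** The only text that fixes when CVnCoV recipients learn their allocation is in the synopsis, under Trial Visits: "Subjects of the CVnCoV treatment arm will be notified of the trial treatment they received at the next planned trial visit/phone call". SAP 8.3 has the same rule. For placebo recipients, Section 9.1.4.2 says: "Subjects of the placebo treatment arm will be notified of the trial treatment they received by a Subject Information Letter".

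The open-label schedule (Tables 4 and 5) has two contacts: OL-1 at Day 302 and OL-2 at Day 393, the end of trial. Section 9.1.4.1.1 provides for subjects already past the first: "If the Day 302 phone call was already performed as part of the randomized observer-blinded phase before approval of Protocol version 4.0", then "the ICF will be signed at the Day 393/EOT phone call/clinic visit". Footnote a of Tables 4 and 5 says the same. SAP Table 5 (Section 10.2) confirms that for a site unblinded after Day 302 but before Day 393, Day 302 is not replaced by OL-1 and Day 393 is replaced by OL-2.

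In Table 4 the AV-advice row is marked in the OL-1 column only. Confirming the AV choice is listed only under OL-1 (9.1.4.1.1). The OL-2 list (9.1.4.1.2) has neither step.

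Two general duties carry no date. Section 7.3.3.2: "Each subject will be informed by the Investigator of the available results and whether he/she received CVnCoV or placebo in the trial", with a reference to 9.1.4. Section 7.1.2.3 says investigators will inform subjects, after unblinding, of their treatment and of the AVs available in the country.

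**The concern.** The amendment's first stated purpose is to unblind the remaining subjects and tell them what they received. Section 9.1.4.1 adds that CVnCoV subjects "who did not yet receive an AV will have to decide whether they will opt to receive an AV". That decision needs the allocation and AV information while it can still be acted on.

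For a still-blinded CVnCoV subject past the Day 302 call, the next planned contact is the last one. A site that follows the timing sentence as written tells the subject at trial exit, and no scheduled step before then raises an AV. Placebo subjects, who leave the trial, are sent a letter, while the subjects kept in follow-up may wait longer. The trial had by then reported 48% overall efficacy, with efficacy not established over age 60 (3.1.4), and the sponsor had withdrawn the product from EMA review.

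**Working it through.** **Inputs**
- Contact days: Table 4 gives 29 + 273 = 302 and 29 + 364 = 393. Both reproduce.
- Windows: blinded-phase Day 302 call −7/+7 (9.1.1.9, 9.1.2.9, 9.1.3.6); OL-2 −0/+21 (Table 4).
- Trial Day = date − date of first vaccination + 1 (SAP 10.2).
- The open-label phase starts on approval per country or site (9.1.4), whatever the subject's trial day.

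**Who is affected.** Still-blinded CVnCoV subjects whose Day 302 call is done and whose Day 393 has not arrived at approval: nominally Trial Day 302 to 392.

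**Nominal wait from site unblinding to notification**
- Wait = 393 − Trial Day at approval.
- Trial Day 302: 393 − 302 = 91 days. Trial Day 392: 393 − 392 = 1 day.
- If first-dose dates are spread evenly over the band (assumption), the mean is (1 + 91)/2 = 46 days.

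**With visit windows**
- Earliest blinded call: 302 − 7 = Day 295. Latest OL-2: 393 + 21 = Day 414.
- From the call: 414 − 295 = 119 days at most.
- From site unblinding, with approval the day after that call (Day 296): 414 − 296 = 118 days at most.

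**Subjects not yet at Day 302.** Those past Day 211 (Trial Day 212 to 301 at approval) do have OL-1, but wait 302 − Trial Day = 90 down to 1 day for it. They are not left until exit.

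**Is the band realistic?** Approval dates are not given. SAP version 5.0, dated 10 Mar 2022, says it was written before all authorities had approved version 4.0. Taking 10 Mar 2022 as one site's approval date (assumption):
- The band is first doses 391 to 301 days earlier: 12 Feb to 13 May 2021.
- SAP Table 10 provides for randomisation dates around 9 to 16 Apr 2021 at one site, inside this band. With the first dose on the randomisation date (assumption), these are Trial Day 336 and 329 on 10 Mar 2022: 393 − 336 = 57 and 393 − 329 = 64 days before Day 393.
- That site serves only to date randomisation. Its subjects carry specially assigned unblinding dates and are not counted as affected.

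**How many?** Not derivable. The number lies within the CVnCoV share of the roughly 20% of subjects still blinded on 18 Nov 2021 (100% minus nearly 80%), a ceiling already 112 days old on 10 Mar 2022.

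**The case against.** The strongest counter-text is Section 7.1.2.3. It ties treatment and AV information to trial unblinding, not to OL-1, and does so to let subjects make an informed decision. That aim is defeated if the information comes at exit. Section 7.3.3.2 says each subject will be informed, 5.1.3 says subjects choosing an AV will be recommended to obtain one, and 12.4 requires new relevant information to be passed on. Sites hold what they need: "Sites will be provided with a list of treatment assignments for subjects who are still blinded at the timepoint of trial unblinding". These are real obligations, and a conscientious site could inform everyone promptly. But none sets a date or adds a contact, and 7.3.3.2 points to 9.1.4, whose Section 9.1.4.1 gives CVnCoV subjects no notification route of its own. The one sentence with a time in it is the synopsis sentence.

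Access to an AV does not depend on notification either. Subjects could ask for individual unblinding, AVs were allowed under national programmes (7.6.2), and AE or COVID-19 reports create unscheduled contacts. Investigators had been advised to discuss an AV with subjects aged 60 and over (3.1.4). This narrows the gap, mainly to younger subjects who do not ask, but does not close it.

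SAP 10.6.1 mentions an Urgent Safety Measure of 30 Nov 2021. Its content is not in these documents and may have told subjects more. A conversation may also suit subjects who are asked to stay and consent, but a letter at unblinding does not prevent a later conversation.

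The timing of consent is not itself a defect: OL-2 lists the ICF first and no scheduled open-label procedure comes before it.

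**Conclusion.** The concern holds, within the limits of scheduled contacts and the planned route. Still-blinded CVnCoV subjects past the Day 302 call at approval have Day 393/EOT as their only planned open-label contact. The rule as written has them told then, 1 to 91 days after site unblinding nominally and up to 118 days with windows. AV advice has no slot for them, even at Day 393.

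This rests on the schedule in both documents. It does not establish how many subjects were affected or what sites did in practice; enrolment dates, approval dates and the arm split of blinded subjects are not given. The analysis effect is negligible: cohorts are assigned retrospectively from AV records (SAP 9.6.8), and the analyses in SAP 12.7.7 replace those of the open-label safety endpoints. It should be fixed because it concerns what participants are told and the remedy is simple.

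**What to change.** **Main change.** Replace the timing sentence in the synopsis and in SAP 8.3, and add the same text to Section 9.1.4.1:

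*At site unblinding, every CVnCoV recipient who is still blinded will be sent a Subject Information Letter stating the treatment received and the AVs available in the country.*

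This covers subjects past Day 302 and also those who would otherwise wait for OL-1.

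**Optional change.** In footnote a of Tables 4 and 5, and in 9.1.4.1.1 and 9.1.4.1.2, allow subjects whose Day 302 call preceded approval to sign the ICF remotely when they receive the letter, keeping Day 393/EOT as the fallback. The main change does not depend on this.

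**Cost.** A few sentences in the protocol and SAP, one mailing per still-blinded CVnCoV subject, and some remote consent handling if the option is taken. The treatment lists (9.1.4), a letter procedure (9.1.4.2) and remote signature (Tables 4 and 5, footnote a) are already in the plan.

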2 STUDY SCHEMATIC AND SCHEDULE OF ACTIVITIES

Figure 1 Overview of HERALD Trial CV-NCOV-004

AV: authorized/licensed vaccines for preventing COVID-19; i.m.: intramuscular; SoC: standard of care.

Clinical Trial Protocol	CV-NCOV-004
CureVac AG	COVID-19 mRNA Vaccine

	Vaccination Period						Follow-up Period			
	Clinic Visit	Phone Call	Clinic Visit	Phone Call	Clinic Visit		Clinic Vis	it	Phone Call	Clinic Visit
Clinic Visit Number	1 ª	-	2	-	3	4	5	6	-	7
Visit Window (days)	n/a	-0/+0	-3/+7	-0/+0	-3/+3	-3/+7	-7/+7	-7/+7	-7/+7	-0/+21
Trial Day	1	2	29	30	43	57	120	211	302	393
Vaccination Day (Reference for post-vaccination time points)	-	1	1	29	29+14	29+28	29+91	29+182	29+273	29+364
Visit Week (Wk) / Month (M)			Wk 4		Wk 6	Wk 8	M 4	M 7	M 10	M 13
Signed informed consent	Х									
Inclusion/exclusion criteria	Х									
Demographics	Х									
Smoking information	Х									
Medical history	Х									
Medication/vaccination history ^b	Х									
Pregnancy test⁰	Х		Х							
Trial Vaccination										
Review criteria for delay or cancellation of trial vaccination ^d	Х		х							
Randomization	Х									
Administration of CVnCoV or placebo (observer-blinded administration)	х		х							
Safety Monitoring										
Physical examination ^e	Х									Х
Symptom-directed physical examination ^e			Х		Х	Х	Х	Х		
Vital signs ^{e,f}	Xf		Xf		Х	Х	Х	Х		Х
eDiary collection of solicited local and systemic reaction data, and unsolicited AEs ⁹	Х	х	х	х	Х	х				
Collection of following AEs:										
Medically-attended AEs ^h	Х	Х	Х	Х	Х	Х	Х	Х		

Table 1 Schedule of Trial Assessments and Procedures for Phase 2b - Immunogenicity Subset

Clinical Trial Protocol CureVac AG

	Vaccination Period					Follow-up Period				End of Trial
	Clinic Visit	Phone Call	Clinic Visit	Phone Call	Clinic Visit		Clinic Visi	t	Phone Call	Clinic Visit
Clinic Visit Number	1ª	-	2	-	3	4	5	6	-	7
Visit Window (days)	n/a	-0/+0	-3/+7	-0/+0	-3/+3	-3/+7	-7/+7	-7/+7	-7/+7	-0/+21
Trial Day	1	2	29	30	43	57	120	211	302	393
Vaccination Day (Reference for post-vaccination time points)	-	1	1	29	29+14	29+28	29+91	29+182	29+273	29+364
Visit Week (Wk) / Month (M)			Wk 4		Wk 6	Wk 8	M 4	M 7	M 10	M 13
 SAEs and AESIs^h 	Х	Х	Х	Х	Х	Х	Х	Х	Х	Х
 AEs leading to vaccine withdrawal or trial discontinuation^h 	Х	х	Х	х	Х	х	Х	х	х	х
Concomitant medication/vaccination ⁱ	Х	Х	Х	Х	Х	Х	Х	Х	Х	Х
COVID-19 Case Detection										
Case detection and collection of case information ⁱ	Х	Х	Х	Х	Х	Х	Х	Х	Х	Х
Antibody Testing ^k (n=1,200)										
Binding antibody to RBD of S (spike) protein of SARS-CoV-2 (~6 mL blood) ^I	X ^k		X ^k		Х	х	х	х		
SARS-CoV-2 viral neutralizing activity (~6 mL blood) ⁱ	X ^k		Xk		Х	Х	Х	Х		
Binding antibody to the N (nucleocapsid) protein of SARS-CoV-2 (~6 mL blood) ^I	X ^k				Х			х		
Genomic Biomarkers (n=200 at selected sites)										
In subjects from selected site(s): genomic biomarkers (~6 mL whole blood)	X ^k		X ^k		Х		х	х		
Cell-mediated Immunity (n=200 at selected sites)										
In subjects from selected site(s): cell-mediated immunity (~32 mL blood)	X ^k		X ^k		Х		х	х		
Trial End										Х

AE: adverse event; AESI: adverse event of special interest; eCRF: electronic case report form; n/a: not applicable; RBD: receptor-binding domain; SAE: serious adverse event.

a. Procedures to establish subject eligibility may be performed within 21 days prior to trial vaccine administration, unless otherwise indicated. If all information to establish eligibility is available, these procedures can be done on the same day as trial vaccine administration. Eligibility criteria should be reviewed and confirmed prior to trial vaccine administration.

Clinical Trial Protocol	CV-NCOV-004
CureVac AG	COVID-19 mRNA Vaccine

- b. Medication/vaccination history taken within 6 months prior to enrollment should be recorded to establish eligibility.
- c. A urine pregnancy test will be performed before each trial vaccination on Day 1 and Day 29 for women of childbearing potential. Where required by local laws and regulations, the pregnancy test will be performed in blood (3 mL).
- d. See Section 6.3 and Section 8.1 for an overview of the criteria leading to delay or cancellation of vaccine administration. In case of delay, the vaccination should take place within the allowed time windows, if feasible. The reasons for delay or cancellation should be documented in the subject chart.
- e. Physical examination and vital signs must be performed/measured by a qualified healthcare professional. See Section 9.3.6 for an overview of the required assessments.
- f. Vital signs will be measured pre- and post-vaccination prior to discharge. Subjects will be observed for at least 30 minutes following each vaccination. Vital signs must be within normal or clinically non-relevant abnormal ranges or have returned to pre-vaccination values for the subject to be discharged.
- g. eDiary (electronic diary) for recording of post-vaccination solicited AEs will be provided to subjects as needed. Solicited local and systemic AEs occurring on the day of vaccination (Day 1 and Day 29) and for the following 7 days will be recorded by the subject in the eDiary. In addition, the eDiary will serve as a memory aid for the subject to report unsolicited AEs occurring on the day of vaccination (Day 1 and Day 29) and for the following 7 days will be recorded by the subject in the eDiary. In addition, the eDiary will serve as a memory aid for the subject to report unsolicited AEs occurring on the day of vaccination (Day 1 and Day 29) and for the following 28 days. The data will be reviewed with the subject by trial staff at the site visits on Day 29, Day 43, and Day 57. During phone calls, the subject's general well-being will be checked and the subject should be reminded to complete the safety information by eDiary. If the subject reports by phone any concerning local or systemic reactions, or other AEs (e.g., on Day 2 or Day 30), these should be followed-up either by a phone call(s) or by an unscheduled site visit, based on the judgment of the Investigator.
- h. Medically-attended AEs will be collected through 6 months after the second trial vaccination. Medically-attended AEs are defined as AEs with medically-attended visits that are not routine visits for physical examination or vaccination, such as visits for hospitalization, an emergency room visit, or an otherwise unscheduled visit to or from medical personnel (medical doctor) for any reason. SAEs, AESIs, AEs leading to vaccine withdrawal or trial discontinuation, and any non-serious intercurrent condition that may affect the immune response to vaccination will be collected through 1 year after the second trial vaccination. During all site visits and phone calls, trial staff will remind subjects to call the site immediately to report the following: if he/she experiences any concerning medical event; any medically-attended visits that are not routine visits for physical examination or vaccination, such as visits for hospitalization, an emergency room visit, or an otherwise unscheduled visits that are not routine visits for physical examination or vaccination, such as visits for hospitalization, an emergency room visit, or an otherwise unscheduled visit to or from medical personnel (medical doctor) for any reason; or experience a serious medical event, have a change in overall health or be diagnosed with a new medical condition by a doctor. These should be reported regardless of the perceived relationship between the event and the trial vaccine.

Medications associated with any solicited and unsolicited AE, medications for a medically-attended AE, AESI, or SAE, and any immune-suppressive/modulating medication will be documented in the eCRF for the time period specified in Table 6. In case any prohibited medication as defined in Section 7.6.2 was taken by the subject, this needs also be documented in the eCRF.

- i. The eDiary will serve as a memory aid for the subjects to report additional concomitant medication or changes in concomitant medication and the corresponding symptoms. The Investigator needs to transcribe concomitant medication and symptoms if matching the criteria outlined in Table 6 and any new concomitant medication or changes in concomitant medication prescribed for any underlying disease present already at Visit 1.
- j. During all site visits and phone calls, trial staff will remind subjects to contact the site if they have any of the symptoms suggestive of COVID-19. In addition, subjects will be messaged up to twice a week to provide a yes or no response to having COVID-19 symptoms. Those who respond "yes" will be contacted by trial staff for follow-up information if the Investigator considers the symptoms could potentially indicate a COVID-19 case and the process outlined in Section 9.2.1 should be followed.
- k. Blood samples should be collected prior to trial vaccination on Day 1 and Day 29.

Clinical Trial Protocol	CV-NCOV-004
CureVac AG	COVID-19 mRNA Vaccine

I. Binding antibodies to the RBD (receptor-binding domain) of the S (spike) protein and to the N (nucleocapsid) protein of SARS-CoV-2 will be measured by immunoassay. Viral neutralizing antibodies directed against SARS-CoV-2 will be measured by a functional activity assay. The N protein is not a component of the CVnCoV vaccine, but is being measured to determine serostatus of subjects to the SARS-CoV-2 virus (naïve or non-naïve to SARS-CoV-2); distinguish immune responses elicited by infection with SARS-CoV-2 from those induced by CVnCoV vaccination; and determine the occurrence of SARS-CoV-2 infection during the trial.

Clinical Trial Protocol	CV-NCOV-004
CureVac AG	COVID-19 mRNA Vaccine

		Vaccination Period Follow-up Period						End of Trial		
	Clinic Visit	Phone Call	Clinic Visit	Phone Call	Clinic Visit	Phone Call	Clini	c Visit	Phone Call	Clinic Visit
Clinic Visit Number	1ª	-	2	-	3	-	4	5	-	6
Visit Window (days)	n/a	-0/+0	-3/+7	-0/+0	-3/+3	-3/+7	-7/+7	-7/+7	-7/+7	-0/+21
Trial Day	1	2	29	30	43	57	120	211	302	393
Vaccination Day (Reference for post-vaccination time points)	-	1	1	29	29+14	29+28	29+91	29+182	29+273	29+364
Visit Week (Wk) / Month (M)			Wk 4		Wk 6	Wk 8	M 4	M 7	M 10	M 13
Signed informed consent	Х									
Inclusion/exclusion criteria	Х									
Demographics	Х									
Smoking information	Х									
Medical history	Х									
Medication/vaccination history ^b	Х									
Pregnancy test⁰	Х		Х							
Trial Vaccination										
Review criteria for delay or cancellation of trial vaccination ^d	Х		х							
Randomization	Х									
Administration of CVnCoV or placebo (observer-blinded)	х		х							
Safety Monitoring										
Physical examination ^e	Х									Х
Symptom-directed physical examination ^e			Х		Х		Х	Х		
Vital signs ^{e,f}	Xf		Xf		Х		Х	Х		Х
eDiary collection of solicited local and systemic reaction data, and unsolicited AEs ^a	Х	х	х	х	х	х				
Collection of following AEs:										
 Medically-attended AEs^h 	Х	Х	Х	Х	Х	Х	Х	Х		

Table 2 Schedule of Trial Assessments and Procedures for Phase 2b - Non-Immunogenicity Subjects

Clinical Trial Protocol CureVac AG

		Vaccination Period Follow-up Period							iod	End of Trial
	Clinic Visit	Phone Call	Clinic Visit	Phone Call	Clinic Visit	Phone Call	Clini	c Visit	Phone Call	Clinic Visit
Clinic Visit Number	1ª	-	2	-	3	-	4	5	-	6
Visit Window (days)	n/a	-0/+0	-3/+7	-0/+0	-3/+3	-3/+7	-7/+7	-7/+7	-7/+7	-0/+21
Trial Day	1	2	29	30	43	57	120	211	302	393
Vaccination Day (Reference for post-vaccination time points)	-	1	1	29	29+14	29+28	29+91	29+182	29+273	29+364
Visit Week (Wk) / Month (M)			Wk 4		Wk 6	Wk 8	M 4	M 7	M 10	M 13
 SAEs and AESIs^h 	Х	Х	Х	Х	Х	Х	Х	Х	Х	Х
 AEs leading to vaccine withdrawal or trial discontinuation^h 	Х	Х	Х	х	Х	х	х	х	х	х
Concomitant medication/vaccination ⁱ	Х	Х	Х	Х	Х	Х	Х	Х	Х	Х
COVID-19 Case Detection										
Case detection and collection of case information ⁱ	Х	Х	Х	Х	Х	Х	Х	Х	Х	Х
Antibody Testing										
Binding antibody to the N (nucleocapsid) protein of SARS-CoV-2 ^k (~6 mL blood)	X ^k				х			х		
Trial End										х

AE: adverse event; AESI: adverse event of special interest; eCRF: electronic case report form; n/a: not applicable; SAE: serious adverse event.

- a. Procedures to establish subject eligibility may be performed within 21 days prior to trial vaccine administration, unless otherwise indicated. If all information to establish eligibility is available, these procedures can be done on the same day as trial vaccine administration. Eligibility criteria should be reviewed and confirmed prior to trial vaccine administration.
- b. Medication/vaccination history taken within 6 months prior to enrollment should be recorded to establish eligibility.
- c. A urine pregnancy test will be performed before each trial vaccination on Day 1 and Day 29 for women of childbearing potential. Where required by local laws and regulations, the pregnancy test will be performed in blood (3 mL).
- d. See Section 6.3 and Section 8.1 for an overview of the criteria leading to delay or cancellation of vaccine administration. In case of delay, the vaccination should take place within the allowed time windows, if feasible. The reasons for delay or cancellation should be documented in the subject chart.
- e. Physical examination and vital signs must be performed/measured by a qualified healthcare professional. See Section 9.3.6 for an overview of the required assessments.
- f. Vital signs will be measured pre- and post-vaccination prior to discharge. Subjects will be observed for at least 30 minutes following each vaccination. Vital signs must be within normal or clinically non-relevant abnormal ranges or have returned to pre-vaccination values for the subject to be discharged.

Clinical Trial Protocol	CV-NCOV-004
CureVac AG	COVID-19 mRNA Vaccine

- g. eDiary (electronic diary) for recording of post-vaccination solicited AEs will be provided to subjects as needed. Solicited local and systemic AEs occurring on the day of vaccination (Day 1 and Day 29) and for the following 7 days will be recorded by the subject in the eDiary. In addition, the eDiary will serve as a memory aid for the subject to report unsolicited AEs occurring on the day of vaccination (Day 1 and Day 29) and for the following on the day of vaccination (Day 1 and Day 29) and for the following 28 days. The data will be reviewed with the subject by trial staff at the site visits on Day 29, Day 43, and Day 57. During phone calls, the subject's general well-being will be checked and the subject should be reminded to complete the safety information by eDiary. If the subject reports by phone any concerning local or systemic reactions, or other AEs (e.g., on Day 2 or Day 30), these should be followed-up either by a phone call(s) or by an unscheduled site visit based on the judgment of the Investigator.
- h. Medically-attended AEs will be collected through 6 months after the second trial vaccination. Medically-attended AEs are defined as AEs with medically-attended visits that are not routine visits for physical examination or vaccination, such as visits for hospitalization, an emergency room visit, or an otherwise unscheduled visit to or from medical personnel (medical doctor) for any reason. SAEs, AESIs, AEs leading to vaccine withdrawal or trial discontinuation, and any non-serious intercurrent condition that may affect the immune response to vaccination will be collected through 1 year after the second trial vaccination. During all site visits and phone calls, trial staff will remind subjects to call the site immediately to report the following: if he/she experiences any concerning medical event; any medically-attended visits that are not routine visits for physical examination or vaccination, such as visits for hospitalization, an emergency room visit, or an otherwise unscheduled visits that are not routine visits for physical examination or vaccination, such as visits for hospitalization, an emergency room visit, or an otherwise unscheduled visits that are not routine visits for physical examination or vaccination, such as visits for hospitalization, an emergency room visit, or an otherwise unscheduled visit to or from medical personnel (medical doctor) for any reason; or experience a serious medical event, have a change in overall health or be diagnosed with a new medical condition by a doctor. These should be reported regardless of the perceived relationship between the event and the trial vaccine.

Medications associated with any solicited and unsolicited AE, medications for a medically-attended AE, AESI, or SAE, and any immune-suppressive/modulating medication will be documented in the eCRF for the time period specified in Table 6. In case any prohibited medication as defined in Section 7.6.2 was taken by the subject, this needs also be documented in the eCRF.

- i. The eDiary will serve as a memory aid for the subjects to report additional concomitant medication or changes in concomitant medication and the corresponding symptoms. The Investigator needs to transcribe concomitant medication and symptoms if matching the criteria outlined in Table 6 and any new concomitant medication or changes in concomitant medication prescribed for any underlying disease present already at Visit 1.
- j. During all site visits and phone calls, trial staff will remind subjects to contact the site if they have any of the symptoms suggestive of COVID-19. In addition, subjects will be messaged up to twice a week to provide a yes or no response to having COVID-19 symptoms. Those who respond "yes" will be contacted by trial staff for follow-up information if the Investigator considers the symptoms could potentially indicate a COVID-19 case and the process outlined in Section 9.2.1 should be followed.
- k. Binding antibodies to the N (nucleocapsid) protein of SARS-CoV-2 will be measured by immunoassay. The N protein is not a component of the CVnCoV vaccine, but is being measured to determine serostatus of subjects to the SARS-CoV-2 virus (naïve or non-naïve to SARS-CoV-2) and the occurrence of SARS-CoV-2 infection during the trial. The baseline blood sample should be collected prior to trial vaccination on Day 1.
- I. Blood samples should be collected prior to trial vaccination on Day 1 and Day 29.

Clinical Trial Protocol	CV-NCOV-004
CureVac AG	COVID-19 mRNA Vaccine

Table 3 Schedule of Trial Assessments and Procedures for Phase 3

	Vaccination Period Follow-up Period					d	End of Trial	
		Clinic Visit		Phone Call	Phone Call	Clinic Visit	Phone Call	Clinic Visit
Clinic Visit Number	1ª	2	3	-	-	4	-	5
Visit Window (days)	n/a	-3/+7	-3/+3	-3/+7	-7/+7	-7/+7	-7/+7	-0/+21
Trial Day	1	29	43	57	120	211	302	393
Vaccination Day (Reference for post-vaccination time points)	-	1	29+14	29+28	29+91	29+182	29+273	29+364
Visit Week (Wk) / Month (M)		Wk 4	Wk 6	Wk 8	M 4	M 7	M 10	M 13
Signed informed consent	Х							
Inclusion/exclusion criteria	Х							
Demographics	Х							
Smoking information	Х							
Medical history	Х							
Medication/vaccination history ^b	Х							
Pregnancy test⁰	Х	Х						
Trial Vaccination								
Review criteria for delay or cancellation of trial vaccination ^d	Х	x						
Randomization	Х							
Administration of CVnCoV or control vaccine (observer- blinded)	Х	x						
Safety Monitoring								
Physical examination ^e	Х							Х
Symptom-directed physical examination ^e		Х	Х			Х		
Vital signs ^{e,f}	Xf	Xf	Х			Х		Х
Collection of following AEs:								
Medically-attended AEs ^a	Х	Х	Х	Х	Х	Х		
SAEs and AESIs ^g	Х	х	Х	х	Х	Х	Х	Х

Version 4.0 (25 November 2021)

Clinical Trial Protocol CureVac AG

		Vaccination Period Follow-up Period						End of Trial
		Clinic Visit		Phone Call	Phone Call	Clinic Visit	Phone Call	Clinic Visit
Clinic Visit Number	1ª	2	3	-	-	4	-	5
